5.1 EFFICACY/EFFECTIVENESS ENDPOINT(S)

Medication compliance (persistence, discontinuation, adherence) along with recurrence are main primary efficacy endpoints and they are defined as follows:

1. MPR (medication possession ratio)
For each of 11 study drugs, the MPR will be calculated by (Days of medication possession from the prescriptions filled in the 180 days) / (180 days + extra days of drug supply from the last prescription fill during the 180 days)
2. Persistence
For each of 11 study drugs, the average length of treatment on the index drug during the first 180 day period (allowing 14 day permissible gap) will be

PFIZER CONFIDENTIAL

calculated. Switching, combination, augmentation, discontinuation will terminate the persistent period.

3. Discontinuation

For each of 11 study drugs chosen as index drug, the percentage of discontinuation in the first 90 days from the index date (acute treatment phase) will be measured (allowing 14 day permissible gap)

4. Adherence

For each of 11 study drugs chosen as index drug, adherence will be measured by MPR and persistence during the first 90 day and 180 day from the index date, respectively (acute treatment phase). MPR ≥ 0.75 and persistence ≥ 90 will be considered as adherence.

* For those period with any identified adverse outcome such as GI bleeding will be considered as a non-adherent period.

5. Recurrence

Recurrence during the acute treatment phase was operationally defined as either one of the following being satisfied:

- 1) Inpatient episode with a diagnosis code in Table 1
- 2) Inpatient episodes via the department of psychiatry or emergency medicine
- 3) Inpatient episode via nursing hospital
- 4) Emergency room visit with a diagnosis code in Table 1
- 5) Suicide attempt identified by the following KCD-7 codes:
 - T40 Poisoning by narcotics and psychodysleptics [hallucinogens]
 - T41 Poisoning by anaesthetics and therapeutic gases
 - T42 Poisoning by antiepileptic, sedative-hypnotic and antiparkinsonism drugs
 - T43 Poisoning by psychotropic drugs, not elsewhere classified
 - T54 Toxic effect of corrosive substances
 - T60 Toxic effect of pesticides
 - X60-X84 intentional self harm
- 6) Augmentation of the following non-AD drugs
 - Antipsychotic: amisulpride, aripiprazole, olanzapine, quetiapine, risperidone, perphenazine
 - Anticonvulsant: carbamazepine, valproic acid, lamotrigine
 - Mood stabilizer: lithium
 - Anxiolytic: buspirone
 - Thyroid hormone: levothyroxine, liothyronine

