Persistence	Primary outcome	HIRA Database	
For each of 11 study drugs, the average length of treatment on the index drug during the first 180 day period (allowing 14 day permissible gap) will be calculated
 
Switching, combination, augmentation, discontinuation will terminate the persistent period

Discontinuation	Primary outcome	HIRA Database	For each of 11 study drugs chosen as index drug, the percentage of discontinuation in the first 90 days from the index date (acute treatment phase) will be measured (allowing 14 day permissible gap)
Adherence	Primary outcome	HIRA Database	
For each of 11 study drugs chosen as index drug, adherence will be measured by MPR and persistence during the first 90 day and 180 day period from the index date, respectively (acute treatment phase). MPR ≥ 0.75 and persistence ≥ 90 will be considered as adherence.
 
* For those period with any identified adverse outcome such as GI bleeding will be considered as non-adherent period

Drug utilization pattern in acute phase	Secondary outcome	HIRA Database	
During the first 90 day period starting from the index date, the following types of drug utilization pattern is recorded
 
- monotherapy (kept on the index medication)- switching (switched to other antidepressant)- combination (adding other antidepressant)- augmentation (adding other non-AD drug such as antipsychotic)
Drug utilization pattern in maintenance phase	Secondary outcome	HIRA Database	
During the second 90 day period (91 ~ 180 days) starting from the index date, the following types of drug utilization pattern is recorded
 
- choice of antidepressant- monotherapy (kept on the same medication)- switching (switched to other antidepressant)- combination (adding other antidepressant)- augmentation (adding other non-AD drug such as antipsychotic)

PFIZER CONFIDENTIAL

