Comorbidities	Covariates	HIRA Database	
The following comorbidities which may affect the drug utilization patterns of antidepressants will be operationally defined using KCD-7 diagnosis codes in medical claims
 
 - Psychiatric comorbidities: panic disorder (F41.0), bipolar disorder (F31), PTSD (F43.1), acute stress (F43.0), personality disorder (F60-69), GAD (generalized anxiety disorder) (F41.1), adjustment disorder (F43.2), sleep disorder (F51), g470, f108), dementia (F00-F03, G30), OCD (obsessive compulsive disorder) ((F42), F429, F605, F428), substance related disorders (F10-19), schizophrenia (F20-29), eating disorder (F50), sexual dysfuntion (F52), mental retardation (F70-F79), developmental disorder (F80-F89), somatoform disorder F45, eating disorder F50 - Mild cognitive impairment (MCI): diagnosis code F06.7 along with a procedure code for neurocognitive function test FB001-FB060* - Charlson Comorbidity Index (CCI)
Non-pharmacologic treatments	Covariates	HIRA Database	
The following non-pharmacologic treatments which may affect antidepressant adherence and persistence/discontinuation will be defined using NHI procedure codes* in medical claims
 
 - Individual psychotherapy** NN012 intensive analytic NN013 intensive - Group psychotherapy NN021 general NN022 analytic NN023 psychodrama - Family psychotherapy NN031 individual NN032 group NN040 occupational or recreation therapy NN050 narcoticsynthesis - Electroconvulsive therapy NN071 simple ETC NN072 modified ETC - Continuous sleep treatment NN081 electro sleep treatment NN082 drug induced sleep treatment NN083 sleep treatment with anesthesia NN090 psychiatric rehabilitation NN100 psychiatric emergency treatment - Psychiatric social work NN111 individual history taking NN112 social work guidance NN113 social investigation

PFIZER CONFIDENTIAL

			
NN114 home visiting
 
* Since January 2018, new code system was employed for psychotherapy and expert advisor consensus will be used to align the new codes to the codes above
 
NN001-NN005 individual psychotherapy
 
NN061 Cognitive Behavioral Therapy-Individual
 
NN062 Cognitive Behavioral Therapy-Group
 
** NN011 supportive was excluded since it is more of a routine code used for majority of patients according to Ahn et al. (2012)¹³

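### Recurrence criterion 6 has no indication condition, so a listed drug newly started for thyroid disease, epilepsy, bipolar disorder or schizophrenia is scored as depression recurrence; the look-back for an added drug is also unstated

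*SAP*

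**What the plan says.** SAP 5.1, item 5, opens with "Recurrence during the acute treatment phase was operationally defined as either one of the following being satisfied", so any single criterion suffices. The sixth is "6) Augmentation of the following non-AD drugs". The list then reads "Antipsychotic: amisulpride, aripiprazole, olanzapine, quetiapine, risperidone, perphenazine"; "Anticonvulsant: carbamazepine, valproic acid, lamotrigine"; "Mood stabilizer: lithium"; buspirone; and "Thyroid hormone: levothyroxine, liothyronine". Criteria 1 to 6 carry over unchanged to the period after the acute phase, and Table 3 (SAP 5.4) repeats the definition.

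For persistence, Table 3 states: "Switching, combination, augmentation, discontinuation will terminate the persistent period". Adherence requires both MPR of at least 0.75 and persistence of at least 90.

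The only description of augmentation itself is in the utilization-pattern rows of Table 3 (and of Protocol 9.3). It is the adding of a non-antidepressant drug, with antipsychotics given as an example.

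The 12-month pre-index exclusions in SAP 4.1 cover the Table 1 depression diagnoses and the Table 2 antidepressants. They do not cover the augmentation drugs.

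**The concern.** Several listed drugs are also treatments for conditions other than depression, and the plan keeps patients with those conditions in the cohort. Criterion 6 does not ask what the drug was started for, so a prescription unrelated to mood can be recorded as depression recurrence. SAP 5.1 names medication compliance and recurrence as the main primary effectiveness endpoints, and augmentation enters both. False events would inflate recurrence and shorten persistence. They could also distort comparisons between antidepressants if some are chosen more often for patients with these comorbidities.

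**Working it through.** **1. Conditions written for each endpoint that uses augmentation**

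| Endpoint | Drugs that count | Indication condition | Look-back for an added drug |
|---|---|---|---|
| Recurrence (SAP 5.1 item 5, Table 3) | Named list in criterion 6 | None | None stated |
| Persistence (SAP 5.1 item 2, Table 3) | No list of its own | None | None stated |
| Utilization pattern (Table 3) | Open wording, antipsychotic as example | None | None stated |
| Adherence (SAP 5.1 item 4) | Through persistence of at least 90 | None | None stated |

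**2. Who is in the cohort.** SAP 4.1 does not exclude bipolar disorder, schizophrenia, epilepsy or thyroid disease. Table 3 lists bipolar disorder (F31) and schizophrenia (F20-29) as covariates. Epilepsy (G40) appears as a safety outcome in SAP 5.2. Table 3's comorbidity row names neither epilepsy nor thyroid disease.

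**3. Three cases under these rules**
- Levothyroxine first claimed after index, for thyroid disease: criterion 6 is met and recurrence is scored. If the same drug is treated as augmentation for persistence, the persistent period ends. If that happens before day 90, the patient is also non-adherent. The one claim can then feed both sides of the recurrence-by-compliance comparison in SAP 7.2.2.
- Valproic acid started after a G40 claim: the patient has a safety outcome and then, for its treatment, a depression recurrence.
- Lithium taken before index and refilled after it: the word for adding suggests it should not count, but no rule says how long the drug must have been absent.

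The first two follow from criterion 6 as written. The third depends on the programmer.

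**4. Size.** The documents give no sample-size, power or event figure that depends on this definition, so there is nothing to reproduce. The following is illustration only. Let p be the true recurrence risk and f the share of patients without recurrence who receive a listed drug for another indication. Both are assumed.

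Observed risk = p + (1 − p) × f. False share of counted recurrences = (1 − p) × f / observed risk.

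| f | p = 5%: observed risk, false share | p = 10%: observed risk, false share |
|---|---|---|
| 1% | 5.95%, 16% | 10.9%, 8% |
| 3% | 7.85%, 36% | 12.7%, 21% |
| 5% | 9.75%, 49% | 14.5%, 31% |
| 10% | 14.5%, 66% | 19.0%, 47% |

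- Same f in both groups, true risks 5% and 10% (true ratio 2.0): the observed ratio is 10.9/5.95 = 1.83 at f = 1%, 12.7/7.85 = 1.62 at 3%, 14.5/9.75 = 1.49 at 5%, and 19.0/14.5 = 1.31 at 10%.
- Different f, no true difference, p = 5%: f of 1% versus 3% gives 7.85/5.95 = 1.32; 3% versus 10% gives 14.5/7.85 = 1.85.
- Different f, no true difference, p = 10%: the same pairs give 12.7/10.9 = 1.17 and 19.0/12.7 = 1.50.

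**5. Feasibility of a look-back.** Data start on 1 January 2017 and intake on 1 January 2018 (SAP 2.1), so every index date has at least 12 months of prior claims.

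**The case against.** A reader might infer that any claim for a listed drug after index is augmentation, so that patients on long-term thyroid hormone or lithium lose persistence at their first refill. The documents do not support that. Table 3 speaks of adding a drug, and SAP 2.2 of changes from initial monotherapy. Both point to a drug new to the regimen. What stands is narrower: the look-back is unwritten, so refills could be counted, but the plan does not say that they are.

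A reader might also scale the earlier study's 752,190 patients over five years (Protocol 9.5) to the 18-month intake, 752,190/60 × 18 = 225,657, and apply an assumed percentage to obtain a number of false augmentations. That is not a supportable estimate. It assumes a constant annual rate and the same eligibility, although the SAP caps age at 70. The documents also give no rate of use for other indications.

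Three further points deserve weight:
- The named list belongs to recurrence only. Its use for persistence and utilization pattern is an inference from wider wording.
- SAP 7.1 plans propensity-score matching and weighting, with comorbidities among the covariates. This may reduce differential error for F31 and F20-29. It does not correct a misclassified outcome, and it is less assured for epilepsy and thyroid disease, which the comorbidity row does not name. Protocol 9.7 also has unmatched comparisons reported.
- The objectives are exploratory and SAP 3 states no hypotheses. That lowers the stakes but does not make a thyroid prescription a depression recurrence.

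**Conclusion.** The point holds for indication and, more weakly, for prior use. As written, criterion 6 scores a listed drug newly started for thyroid disease, epilepsy, bipolar disorder or schizophrenia as depression recurrence, in both phases. Under the open wording in Table 3 the same event can end persistence and so reach adherence and utilization pattern. Prior use is an unspecified rule, not a decision to count prior users. The direction of the error in recurrence counts is upward; its size is unknown. The percentages and ratios above rest entirely on assumed p and f and show only that small shares can matter when true recurrence is uncommon. Neither document plans an analysis without criterion 6, and comorbidity subgroups are only optional (SAP 4.4). This should be corrected because it affects primary endpoints and the repair is modest.

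**What to change.** In SAP 5.1 and Table 3, define augmentation once, with one drug list, for persistence, utilization pattern and recurrence:

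- **(a) New use:** no claim for that drug in the 12 months before index.
- **(b) Indication, for recurrence and persistence:** do not count the drug when a matching other-indication code is claimed in a stated window, for example from 12 months before index up to the date the drug is started. The matches are thyroid disease for thyroid hormone; G40 for anticonvulsants; and F31 or F20-29 for lithium, anticonvulsants or antipsychotics. Buspirone would be subject to (a) only.

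Report one sensitivity analysis without filter (b) and one without criterion 6. Removing criterion 6 alone would not be enough, because persistence, adherence and utilization pattern would still use the undefined term.

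The cost is mainly programming. Thyroid-disease codes must be added, since neither document lists them, and their presence in the extract confirmed. Filter (b) will miss some true augmentations in patients with those codes. Protocol 9.9 warns that diagnosis codes are sometimes entered to avoid denial of reimbursement, so a code may not show the real reason for the drug. That is why (b) needs a time window and a result without it. The SAP amendment is dated to the data-analysis stage, so the change should be documented as made then.

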**Study population**

Subjects who newly initiated antidepressant therapies between Jan 01, 2018 to Jun 30, 2019 in the Health Insurance Review and Service (HIRA) database

PFIZER CONFIDENTIAL

* Index date is the first prescription date of study drugs, including SSRIs, SNRIs, and other ADs during the intake period (Jan 01, 2018 to Jun 30, 2019).

Data source

The Korean HIRA claims data covers 97% of Korean population (about 50 million people) in the Korean National Health Insurance and 3% of Korean population in Medical Aid program.

HIRA claims database from January 01, 2017 to December 31, 2020 will be used for the analysis. It contains the data of universal health insurance system in Korea, wherein patient demographic information, inpatient and outpatient service use, pharmacy dispensing claims, and death can be obtained.

[figure not shown]
The main limitation of HIRA data is lack of clinical lab data and other clinical markers since it is a data collected for claims for reimbursement purpose.

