4 ANALYSIS SETS/POPULATIONS

4.1 FULL ANALYSIS SET

Subjects who newly initiated antidepressant therapies between Jan 01, 2018 to Jun 30, 2019 in the Health Insurance Review and Service (HIRA) database

** Index date is the first prescription date of study drugs, including SSRIs, SNRIs, and other ADs during the intake period (Jan 01, 2018 to Jun 30, 2019).*

Inclusion criteria

Patients must meet all of the following inclusion criteria to be eligible for inclusion in the study:

1. *Patients aged 18 years or older and 70 years or younger on the index date*
2. *Patients who had at least one inpatient claim or two outpatient claims in the intake period with any of the following diagnosis codes:*

PFIZER CONFIDENTIAL

Table 1. Diagnosis Codes for Inclusion

KCD-7 Code ¹⁾	Description
F06.3	Organic mood[affective] disorders
F32*	Depressive episode
F33*	Recurrent depressive disorder
F34.1	Neurotic depression
F38.1	Other recurrent mood[affective] disorders
F41.2	Mixed anxiety and depressive disorder

1) KCD-7 = Korean version of ICD-10

3. Patients prescribed any of the following antidepressant during intake period (from January 1, 2018 to June 30, 2019)

Table 2. Study Drug List

Active Ingredient	Dosage	HIRA Drug Main Ingredient Codes
Escitalopram	5mg	474801ATB
	10mg	474802ATB
	20mg	474803ATB
	15mg	474804ATB
	10mg	521101ATD
	20mg	521102ATD
Paroxetine	10mg	209301ATB
	20mg	209302ATB
	12.5mg	209304ATR
	25mg	209305ATR
Fluoxetine	10mg	161501ACH
	10mg	161501ATB
	20mg	161502ACH
	20mg	161502ATB
	20mg	161502ATD
Mirtazapine	15mg	196201ATB
	15mg	196201ATD
	30mg	196202ATB
	30mg	196202ATD
	7.5mg	196204ATB
	7.5mg	196204ATD
Duloxetine	30mg	495501ACE
	30mg	495501ATE
	60mg	495502ACE
	60mg	495502ATE
Sertraline	50mg	227001ATB
	0.1g	227002ATB
Venlafaxine	75mg	247502ACR
	37.5mg	247504ACR
Tianeptine	12.5mg	229601ATB
Vortioxetine	5mg	628501ATB
	10mg	628502ATB
	15mg	628503ATB

PFIZER CONFIDENTIAL

	20mg	628504ATB
Desvenlafaxine	50mg 100mg	626401ATR 626402ATR
Bupropion	0.1g 0.15g 0.3g	428101ATB 428102ATR 428103ATR

Exclusion criteria

1. Patients meeting any of the following criteria will not be included in the study:
2. Patients with a claim of diagnosis codes in Table 1 during the 12 month pre-index period
3. Patients with a claim of prescription in Table 2 during the 12 month pre-index period

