Recurrence after the acute treatment phase was operationally defined as either one of the following being satisfied:

- 1) ~6) the same as above
- 7) AD prescription after 30 days of drug holiday

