7.2.2 Study Drug Analysis in Maintenance Phase

- To understand the top 11 antidepressants usage among the Korean patients with depression in maintenance treatment phase
- Primary analysis
- Endpoints:
 - Choice of study drug
 - Average length of new treatment maintenance
 - Average number of co-medications (e.g., atypical antipsychotics, mood stabilizer, thyroid hormone, psychostimulant) when following changes occur from initial monotherapy: switching, combination, augmentation
 - Medication compliance (adherence, discontinuation, and persistence)
 - Recurrence by each antidepressant, by compliance
 - Risk of adverse events
- Population: patients from the acute treatment phase who started maintenance treatment (after 90 days from the index date)
- Significance on continuous variables will be tested by ANOVA (if equal variance condition satisfied) or Kruskal-Wallis H test (otherwise). Provider specialty and other patient characteristics will be used to fit antidepressant choice by multivariate logistic regression analysis of each study drug choice.
- Covariates: antidepressant class covariates such as SSRIs, SNRIs, and other ADs will be used as grouping variables.
- Missing values will be dropped from the analysis
- The role of this analysis is to provide information on study antidepressants in the maintenance phase of drug therapy for Korean patients with depression.

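### Post-acute recurrence has no stated end day and no clearly assigned time-at-risk method, so crude by-drug percentages may depend on index date

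*SAP*

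**What the plan says.** SAP 5.1 names recurrence, with medication compliance, as a main primary effectiveness endpoint. Item 5 lists six criteria for the acute phase. It then opens the later period with "Recurrence after the acute treatment phase was operationally defined as either one of the following being satisfied" and adds a seventh criterion, "AD prescription after 30 days of drug holiday". Table 3 repeats this. Neither place gives a last day, a horizon or a censoring rule. The neighbouring items do have windows: 180 days for MPR and persistence, 90 days for discontinuation.

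Other passages bear on the window:

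- Table 3 in SAP 5.4 gives a closed maintenance period, "During the second 90 day period (91 ~ 180 days) starting from the index date", but only for the drug utilization pattern.
- SAP 7.2.2 lists "Recurrence by each antidepressant, by compliance" as a maintenance-phase endpoint. Its population is defined only by a start, 90 days after index.
- SAP 4.1 takes index dates "during the intake period (Jan 01, 2018 to Jun 30, 2019"), and SAP 2.1 says "HIRA claims database from January 01, 2017 to December 31, 2020 will be used for the analysis".
- The acute phase is 90 days in the discontinuation item, "in the first 90 days from the index date (acute treatment phase"). The adherence item attaches the same label to a longer period: "first 90 day and 180 day from the index date, respectively (acute treatment phase").

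On method, SAP 7.1 gives numbers and percentages for categorical variables, with tests such as chi-square. It names major bleeding and stroke for cumulative incidence. It then describes a rate per observed time at risk and an unadjusted Kaplan-Meier curve without saying which outcomes these serve. Protocol 9.7 mentions time-to-event models for safety outcomes only.

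**The concern.** Two analysts could follow this SAP and report very different figures for the same primary endpoint, one over a fixed 90 days and the other over everything up to the end of the extract. SAP section 1 says the amendment was made during data analysis, so an unstated window also leaves room for a choice made after seeing results.

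On the open reading, follow-up is set by the calendar. A patient indexed in January 2018 can show a recurrence for more than twice as long as one indexed in June 2019. A drug whose use grew over the intake period would have later index dates, shorter follow-up and a lower crude percentage at the same underlying rate. Neither index date nor length of follow-up is among the Table 3 covariates, so matching or weighting on that list would not correct this. The seventh criterion keeps accumulating events for as long as the window stays open.

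**Working it through.** The documents state no recurrence rate, event count or follow-up length for recurrence, so there is no plan figure to reproduce.

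**Length of observation (from the documents).** Data end on 31 December 2020; index dates run from 1 January 2018 to 30 June 2019.

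| Index date | Days to end of data | After day 90 | After day 180 |
|---|---|---|---|
| 1 Jan 2018 | 1095 | 1005 | 915 |
| 30 Jun 2019 | 550 | 460 | 370 |

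The ratio is 1005/460 = 2.2. The last column applies if the acute phase is taken as 180 days. Every index date has at least 550 days of data before death or loss.

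**Effect on a crude percentage (assumed rates).** Assume a constant hazard and no death or loss. With annual risk p, h = -ln(1 - p)/365 per day, and the expected percentage after t days is 1 - exp(-ht). For p = 0.20, h = 0.000611.

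| Assumed annual risk | 90 days (days 91-180) | 460 days | 1005 days |
|---|---|---|---|
| 10% | 2.6% | 12.4% | 25.2% |
| 20% | 5.4% | 24.5% | 45.9% |
| 30% | 8.4% | 36.2% | 62.5% |

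The last two columns compare the last and first index day. They do not compare two drugs.

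**Effect on a comparison of two drugs with equal risk.**

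- Same index-date mix in both drugs: no difference.
- One drug with flat uptake, the other with uptake growing linearly over the 545 days of intake. Average 1 - exp(-hT) over T = 1005 - s, for s = 0 to 545, with weight 1 + g·s/545. At 20% per year the flat drug shows 35.8%. The growing drug is lower by 0.4 points for 25% growth (g = 0.25), 0.7 points for 50% growth, and 1.2 points if uptake doubles (34.6%).
- Mean index dates three months apart, taken as 686 v 778 days of follow-up: 34.3% v 37.9%, or 3.6 points.

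Across 10%, 20% and 30% per year, the doubling case gives 0.7, 1.2 and 1.5 points. The three-month case gives 2.1, 3.6 and 4.4 points.

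**Could gaps of this size reach the protocol's p < 0.05?** The expected gap equals 1.96 standard errors when n per drug = 1.96² × [p1(1 - p1) + p2(1 - p2)]/(p1 - p2)². For 34.3% v 37.9% this is 3.84 × 0.461/0.036², about 1,370. For 34.6% v 35.8% it is about 12,000. Numbers per drug are not stated. Protocol 9.5 cites 752,190 new users in an earlier five-year HIRA study.

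**The case against.** A reader might infer that patients will be followed for 460 to 1005 days and that by-drug recurrence is therefore not comparable. The documents do not support that, for four reasons.

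1. Recurrence sits under the maintenance-phase analysis, and the only closed maintenance window in the text is days 91-180. On that reading everyone has the same 90 days and the bias disappears. Figure 1 is not shown, and the protocol's amendment log indicates that it carries a follow-up period. This stands, so the defect is an unresolved window. It does not settle the matter: the closed window belongs to another variable, and secondary objective 2 follows treatment to month 9, so day 180 is not a study-wide stop. If the figure shows the end of data, follow-up is still unequal.
2. The person-time and Kaplan-Meier sentences in SAP 7.1 are not expressly limited to bleeding and stroke, and SAP 2.1 speaks of the incidence of recurrence. Nor does any passage assign recurrence a crude percentage with a chi-square test. This stands; the fair statement is that no measure is assigned to recurrence. The curve mentioned is unadjusted, so it would not replace the matched or weighted comparison.
3. SAP 7.1 leaves the final covariate list open, so index date could still be added. True, but nothing commits to it.
4. Unequal follow-up distorts a drug comparison only if index-date mix differs by drug, and the documents give no such distribution. All 11 drugs were chosen as already commonly used. A three-month difference is extreme: with linear growth, it needs one drug flat and the other rising from zero at the start of intake. This stands and limits the likely size.

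SAP section 3 also states no hypotheses or decision rules, so no formal decision rests on this endpoint. It is still a main primary endpoint compared across drugs.

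**Conclusion.** The point holds as an unstated window and an unassigned summary measure for a main primary endpoint. The two readings are 90 days for everyone, or 460 to 1005 days by index date (370 to 915 if the acute phase is 180 days). At an assumed 20% per year these give about 5% against 25-46%.

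Confounding of by-drug percentages by index date is conditional. It needs the open reading, a crude percentage, and uptake that differs between drugs over intake. Under those conditions and a constant 20% per year without death or loss, the spurious difference is about 1 point if one drug's uptake doubles, and about 3.6 points in the extreme three-month case. The true size cannot be read from the documents. The stronger conclusion, that the recurrence results are not comparable between drugs, is not supported. The correction is still worth making, because it costs little and removes both the ambiguity and the conditional bias.

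**What to change.** In SAP 5.1 item 5, Table 3 and 7.2.2:

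- State the day on which the acute phase ends for this endpoint, and compare post-acute recurrence by drug over one horizon common to all patients. Any horizon up to day 550 is available for every index date.
- Report any result that uses data to 31 December 2020 as a person-time rate or a censored time-to-event estimate, not as a crude percentage, and name recurrence among the outcomes for that method in SAP 7.1.
- For recurrence by compliance, count recurrence only after the 180-day MPR and persistence window. With days 91-180, exposure and outcome would overlap: the 30-day holiday in the seventh criterion itself lowers MPR and exceeds the 14-day gap that persistence allows.

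The cost is a few lines of text and a date filter, and no index date is excluded. A fixed horizon counts fewer events, possibly far fewer. At the assumed 20% per year, days 91-180 gives 5.4% against 35.8% for a flat-uptake drug followed to the end of data, so about 85% of events would drop out (1 - 5.4/35.8). A longer common horizon loses fewer, and the person-time or censored analysis keeps them all.
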